3.1.2. PRIMARY SAFETY

- Assessment of adverse events (AEs).
- Potentially significant and clinically important AEs, including adverse events of special interest (AESI), serious adverse events (SAEs), and AEs leading to withdrawal.
- Physical examinations
- Vital signs
- 12-lead electrocardiogram (ECG)
- Clinical safety laboratory tests (hematology, biochemistry, and urinalysis)

3.2. Secondary Endpoints

- Change in modified JDA severity index total skin lesions score (sum of erythema, erythema with pustules, edema) at all study visits
- Change in affected body surface area (BSA) of erythema with pustules, erythema, and edema as measured by modified JDA severity index at all study visits
- Change in total and individual scores in systemic manifestations and laboratory findings as measured by modified JDA severity index at all study visits
- Proportion of subjects achieving a GPPPGA score of 0 or 1 at all study visits
- Change from baseline in GPPPGA scores at all study visits
- Change in PASI score to evaluate a subject's overall plaque psoriasis disease state, if present, at all study visits
- Change in Dermatology Life Quality Index (DLQI) total score at all study visits
- Serum concentration following ANB019 administration.
- Maximum observed concentration (Cmax), time to maximum observed concentration (tmax), area under the concentration-time curve (AUC) and other PK parameters as appropriate
- Presence of anti-drug antibodies (ADA) compared to baseline

3.3. EXPLORATORY ENDPOINTS

- Skin biopsy biomarkers (including but not limited to IL-17, IL-23, IL-8, dendritic cells, epidermal thickness, and leukocytes infiltration)
- Changes in serum cytokines as compared to Baseline at Weeks 1, 4, 8, 12, 16, and 24
- Photographic documentation of lesions
- Optional genetic testing (DNA and mRNA)

4. Hypothesis

No formal hypothesis testing will be performed.

5. STUDY DESIGN

5.1. GENERAL DESCRIPTION

This is an open-label, single arm, multiple dose study to assess the clinical efficacy, as well as the safety, tolerability, and PK of multiple doses of ANB019 in subjects with GPP.

The screening period will be up to 42 days (6 weeks) prior to administration of study drug on Day 1. Written informed consent will be obtained from each subject prior to initiating any study related procedures. All screening procedures will be conducted in accordance with the Schedule of Activities (see Section 1.3 in the protocol). On Day 1, subjects who meet the entry criteria will receive a 750 mg IV dose of ANB019 in an open-label manner, followed by 3 doses of 100 mg SC administered on Days 29, 57, and 85.

Subjects will leave the study center after completion of the 5 hours postdose assessments following IV administration and the 3 hours postdose assessments after the first and second SC injections and with the investigator's approval. Subjects with any ongoing AEs or SAEs at the time of scheduled discharge from the study center should remain at the study center until the Investigator has determined that these events have resolved or are deemed as not clinically significant.

After completing Day 1 assessments, the subjects will return to the study center for follow-up visits on Days 3, 8, weekly from Day 8 to Day 29, every other week up to Day 85, then monthly for 12 weeks to monitor changes in disease activity, safety, and tolerability. In addition, subjects will be contacted via phone by study staff to assess for safety (e.g., AEs and changes in concomitant medications) on Days 36, 50, 64, and 78.

Subjects who are non-responders at Week 4 will be early terminated 4 weeks after the 750 mg IV dose administration. A non-responder is defined as a subject who experiences:

- "No change" on Clinical Global Impression (CGI): 0 points change in JDA total score and not meeting "other criteria" for minimally improved.
- "Worsened" based on CGI: ≥1-point increase in JDA total score.

[figure not shown]
Disease activity (response to study treatment) will be evaluated using the CGI scale according to the mJDA severity index, change in total area of erythema with pustules, erythema, and edema as measured by modified JDA index, systemic manifestations and laboratory findings as per modified JDA severity index, GPPPGA scale, and PASI score (if PP is present). Quality of life (QoL) will be assessed using the DLQI.

Serum samples for PK and immunogenicity will be collected before the administration of ANB019 and at the other time points specified in the Schedule of Activities (see Section 1.3 in the protocol). Refer to Table 2 in the protocol for additional information on sample collection and time points. All subjects enrolled in the study will be asked to participate in the skin biopsy and/or genetic analysis; however, participation is optional, and subjects will be asked to give specific consent for these assessments.

Safety assessments including AE/SAE monitoring, vital signs measurements, physical examination, ECGs, laboratory measurements, and urine assessments will be performed during the study.

The EOS visit will be on Day 169 and all subjects will return to the study center for the EOS procedures (see Section 1.3 in the protocol and Figure 1 below for more details).

Figure 1. Study Schema

Abbreviations: BSL = baseline; IV = intravenous, SC = subcutaneous.

5.2. SAMPLE SIZE

The sample size is not based on statistical power considerations. Approximately 10 subjects will be enrolled at 8 study centers for study treatment.

5.3. Schedule of Activities

Please refer to Section 1.3 in the protocol

5.4. CHANGES TO ANALYSIS FROM PROTOCOL

There are no changes from the analysis mentioned in the protocol.

6. STATISTICAL GENERAL CONSIDERATIONS

All data listings, summaries, and analyses will be performed under the guidance and approval of the Sponsor with this SAP.

Coding of AEs and medical history will be done by Medical Dictionary for Regulatory Activities (MedDRA) directory Version 22 (or higher) and medications data by the World Health Organization (WHO)-drug dictionary dated Mar2019 (or higher) by

The default summary statistics for continuous variables include number of contributing observations (n), mean,

standard deviation (SD), median, minimum, and maximum or as described in the respective section. For categorical variables, the number and percentage (the percentage of subjects in each category relative to the total number of subjects in the relevant analysis set, or relative to the total number of subjects in the relevant analysis set and with assessments available [where appropriate]) in each category will be the default summary presentation.

In general, for non-PK data, the number of decimal places displayed for each statistic will be determined as follows:

- Mean and median: 1 more than the number of decimal places allotted in the raw data received from data management.
- SD: 2 more than the number of decimal places allotted in the raw data.
- Minimum and maximum: equal to the number of decimal places allotted in the raw data.
- Percentages: All percentages between 0 and 100 will be rounded to 1 decimal unless there is a need to report more than 1 decimal for percentages.
- Reference ranges will be reported to the same number of decimal places displayed by the laboratory.
- *P* values and confidence intervals (CIs), if any, will be reported to 4 decimal places. *P* values less than 0.0001 will be presented as "<0.0001" and *p* value greater than 0.9999 will be presented as "1.0000".

Data from subjects excluded from an analysis set will be included in the data listings, but not in the summaries. Concentration versus time summaries will be presented for all subjects in the PK Analysis Set (PKAS). Reporting standards for PK data (ANB019 concentrations) is described in Section 18.

7. PLANNED ANALYSES

7.1. DATA MONITORING COMMITTEE

No Data Monitoring Committee is planned for this study.

7.2. INTERIM ANALYSIS

An interim analysis will be performed when approximately 50% of subjects have completed their Week 4 visit or when at least 2 subjects have reached 16 weeks postdosing. The interim analysis will assess primary efficacy and all safety data. Data from interim analyses might be used as a guideline for possible protocol modifications and planning of future clinical studies.

7.3. FINAL ANALYSIS

Final analysis will be performed once all subjects complete the efficacy, safety, PK and immunogenicity evaluations described in the protocol.

Planned analyses identified in this SAP will be performed by Biostatistics following AnaptysBio authorization of this SAP.

8. ANALYSIS SETS

Agreement and authorization of subjects included/excluded from each analysis set (Table A below) will be conducted in preparation for the IA to be performed when at least 50% of subjects complete their safety and efficacy Week 4 assessments, or at least 2 subjects have completed their Week 16 assessments, and again after all subjects have completed the study for the final analysis.

The FAS analysis set will include all subjects, regardless of whether or Full Analysis Set (FAS) not the treatment was received. Subjects will be analyzed based on treatment received. Safety Analysis Set (SAF) The Safety analysis set will include all enrolled subjects who received at least 1 dose of ANB019. The Safety Analysis Set will be used for all safety analyses. Subjects will be analyzed as treated. Per Protocol Analysis Set The Per Protocol analysis set will include all subjects in the FAS analysis set who do not have major protocol violations that would (PPS) affect the evaluation of the primary efficacy endpoint. The PK analysis set will include all subjects in the Safety analysis set PK Analysis Set (PKAS) who have at least 1 quantifiable PK sample available and who do not have events or deviations with the potential to affect PK concentrations. The PK analysis set will be used for all PK analyses.

Table A. Analysis Sets

8.1. REFERENCE DATES AND STUDY DAY

Study Day will be calculated from the reference start date and will be used to show start/stop day of assessments and events. The Reference start date (Day 1) is defined as the day of the first dose of study medication and will appear in every listing where an assessment date or event date appears.

If the date of the event is on or after the reference date, then:

Study Day = (date of event – reference date) + 1

If the date of the event is prior to the reference date, then:

Study Day = (date of event – reference date)

In the situation where the event date is partial or missing, Study Day and any corresponding durations will appear partial or missing in the listings.

8.2. BASELINE

Unless otherwise specified, Baseline is defined as the last non-missing measurement taken prior to the Reference Start Date and time (including unscheduled assessments).

Where the last non-missing measurement and the Reference Start Date coincide, that measurement will be considered pre-Baseline unless there is conclusive evidence that the measurement was post study treatment administration.

Adverse events (AEs) and medications commencing on the Reference Start Date will be considered post-Baseline.

On Day 1 all assessments, except for the post-dose PK samples, should be taken before study treatment administration.

8.3. RETESTS, UNSCHEDULED VISITS AND EARLY DISCONTINUATION

In general, for by-visit summaries and figures, data recorded at the nominal visit will be presented. In the

event of a retest of the same sample due to e.g. a laboratory error (same visit number assigned), the last usable assessment will be used. Unscheduled measurements will not be included in by-visit summaries, but will contribute to the Baseline, EOS, End of Treatment (EOT) and Last Observation Carried Forward (LOCF) values, or best/worst case value where required (e.g. shift tables).

Listings will include scheduled, unscheduled and early discontinuation data, with unscheduled visits sorted chronologically.

8.4. WINDOWING CONVENTIONS

Visit windows are assigned based on the Protocol SOA, and are presented in

Table B. Visit Windows

Table B.	Visit	Windows
----------	-------	---------

Assigned Visit	Assigned Study Week	SOA day(s)	Study day(s)
D1/W0 (Screening)	-42 to 0	-28 to 0	-42 to 0
D1-W0 (Treatment)	0	0	1
D3-W1 (Treatment)	1	0	3
D8-W1 (Treatment)	1	0	8
D15-W2 (Treatment)	2	±1	15
D22-W3 (Treatment)	3	±1	22
D29-W4 (Treatment)	4	±2	29
D36-W5 (Treatment)	5	±2	36
D43-W6 (Treatment)	6	±2	43
D50-W7 (Treatment)	7	±2	50

Assigned Visit	Assigned St Week	udy SOA day(s)	Study day(s)
D57-W8 (Treatment)	8	±2	57
D64-W9 (Treatment)	9	±2	64
D71-W10 (Treatment)	10	±2	71
D78-W11 (Treatment)	11	±2	78
D85-W12 (Treatment)	12	±2	85
D113-W16 (Follow up)	16	±2	113
D141-W20 (Follow up)	20	±2	141
D169-W24/EOS/ET (Follow up)	24	±2	169

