### **7.2 Subject Discontinuation/Withdrawal from the Study**

A subject may withdraw from the study at any time at his/her own request, or may be withdrawn at any time at the discretion of the Investigator for safety, behavioral, compliance, or administrative reasons.

In case of early withdrawal from the study drug and study, the subject will be required to attend the ET visit (see the Schedule of Activities in Section 1.3). Subjects must be withdrawn from the study under the following circumstances, any significant AE which in the opinion of the Investigator is related to the study drug or SAE, or pregnancy occurring through the EOS visit and should be followed-up until outcome:

- Prior to study treatment administration, the Investigator decides that the subject should be withdrawn or is at risk. If this decision is made because of an AE or a clinically significant laboratory value, the study drug should not be administered and appropriate measures are to be taken. AnaptysBio Inc. and/or ██████ is to be notified immediately.
- Significant deviation/lack of compliance with protocol other than the use of excluded/prohibited medications.
- Use of any excluded/prohibited medications that in the opinion of the Investigator necessitates the subject being withdrawn ([Appendix 5](#)).
- Termination of the study by the Investigator or Sponsor.
- Pregnancy ([Appendix 6](#) and Section 8.3.5 Pregnancy).

- New information suggests taking part in the study may not be in the participant's best interest.

If the subject withdraws consent for disclosure of future information, the Sponsor may retain and continue to use any data collected before such a withdrawal of consent.

If a subject withdraws from the study, he/she may request destruction of any samples taken and not tested, and the Investigator must document this in the study center study records.

See Schedule of Activities (Section 1.3) for data to be collected at the time of study discontinuation and follow-up and for any further evaluations that need to be completed.

Subjects withdrawing from the study prematurely for reasons other than a study drug related AE may be replaced at the discretion of the Investigator and Sponsor to ensure the required number of evaluable subjects.

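### SAP Table B puts early-termination visits in the Week 24 row, so on the most direct reading their data are tabulated as Week 24 results

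*SAP*

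**What the plan says.** - **Windows (SAP 8.4, Table B).** "Visit windows are assigned based on the Protocol SOA". The table repeats the Schedule of Activities tolerances of 0, ±1 or ±2 days. ET appears only in the last row, "D169-W24/EOS/ET (Follow up", which is study week 24, Day 169 ±2.
- **Summary rule (SAP 8.3).** "In general, for by-visit summaries and figures, data recorded at the nominal visit will be presented". One class of data is held back: "Unscheduled measurements will not be included in by-visit summaries". Early discontinuation is in the section's heading, but the only statement about such data is "Listings will include scheduled, unscheduled and early discontinuation data, with unscheduled visits sorted chronologically".
- **Early exits.** SAP 5.1: "Subjects who are non-responders at Week 4 will be early terminated 4 weeks after the 750 mg IV dose administration". Protocol 7.2: "In case of early withdrawal from the study drug and study, the subject will be required to attend the ET visit". Footnote b to the Schedule of Activities is softer: it encourages attendance and labels the combined ET/EOS visit as Week 24, Day 169. Protocol 6.7 names the Day 169 visit and the ET visit as alternatives.
- **Output rows (SAP Appendix 1).** Day 169 and End of Study are separate rows. There is no ET row.
- **Missing values.** SAP 17.2.2 leaves missing GPPPGA and other secondary efficacy values missing, except DLQI, which is carried forward. SAP 17.1.2 keeps a Week 4 non-responder as a non-responder at Week 16.

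**The concern.** Early exits are part of this design. Week 4 non-responders must leave, and the protocol gives other routes out. A subject who leaves has an ET visit, and the only label Table B offers for it is the Week 24 row. If programming follows nominal visit, a value recorded about four weeks after the IV dose is averaged with values recorded at 24 weeks. Those from Week 4 terminations all come from non-responders.

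The exposed outputs are the Week 24 or Day 169 summaries of mJDA scores, affected area, GPPPGA, PASI, laboratory values, vital signs and PK concentrations, and the Day 169 paired t-test on cytokines (SAP 19.6.1). With about 10 subjects, one misplaced value is enough to move a mean. For mJDA, GPPPGA and PASI it would also act as a carry-forward that SAP 17.2.2 does not allow.

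**Working it through.** The plan gives no figure to reproduce on this point. The check sets its rules side by side and then sizes the exposure.

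**1. Where does an ET visit on Day 29 go?**

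| Rule | Row assigned |
|---|---|
| Nominal visit (SAP 8.3 with the Table B label) | Week 24/EOS/ET |
| Table B study-day limits | Week 4, because 29 lies in 27 to 31 and not in 167 to 171 |
| SAP Appendix 1 output rows | Unresolved: Day 169 and EOS are separate and there is no ET row |
| SAP 17.2.2, subject gone before Week 24 | Missing at Week 24, except DLQI |

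The first two answers are 169 − 29 = 140 days, or 20 weeks, apart. SAP 8.3 is the only text that says what by-visit summaries use, so the nominal answer is the most direct reading.

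**2. Do the study-day limits settle it?** Days covered by the 17 post-screening rows: 3 rows at ±0 give 3 days, 2 rows at ±1 give 6, and 12 rows at ±2 give 60. The total is 69 of Days 1 to 171, so 171 − 69 = 102 days (60%) lie in no window. These include Days 32–33 and 39–40, soon after the Week 4 visit. Under a study-day rule, an ET visit on Day 33 would have no row. The gaps remove nothing if nominal visit governs.

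**3. Size.** Assume N = 10 (about 10 are planned in SAP 5.2), k subjects terminated early, each with a separate ET record labelled Week 24, and all others completing. The early share of the row is k/10. For illustration only, take a mean mJDA change of −6 in completers and 0 in terminated subjects. The pooled mean is then −6 × (10 − k)/10.

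| k (assumed) | Early share of Week 24 row | Observations near Day 169 | Illustrative pooled mean (completers −6.0) |
|---|---|---|---|
| 0 | 0% | 10 | −6.0 |
| 1 | 10% | 9 | −5.4 |
| 2 | 20% | 8 | −4.8 |
| 3 | 30% | 7 | −4.2 |
| 4 | 40% | 6 | −3.6 |
| 5 | 50% | 5 | −3.0 |

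**4. Which outputs move?** Means and changes from baseline move as in step 3. The proportion with GPPPGA 0 or 1 uses all enrolled subjects as denominator (SAP 17.2.1.4), so it changes only if the ET value itself is 0 or 1. The primary endpoint is read at Weeks 4 and 16 and its rule for Week 4 non-responders does not use Table B. A terminated subject's last DLQI reaches Week 24 by carry-forward, whatever the windows say.

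**The case against.** The strongest reply is that the SAP nowhere says ET data are Week 24 data. Table B's ±2 days would exclude a Day 29 visit. Appendix 1 gives EOS its own row, and SAP 8.3 treats EOS as a value apart from by-visit summaries, so an ET record could go there and leave Day 169 untouched. Footnote b could even mean that the ET visit is held at Day 169. This stands in part: tabulation as Week 24 is the most direct reading, not a stated rule. It does not clear the plan, because these texts point to different rows and none is said to prevail.

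Four stronger readings are tempting, and the documents do not support them:

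- **The window gaps lose data.** They do so only if study day assigns visits. Under the nominal-visit rule they drop nothing, so the gaps and the Week 24 misplacement belong to alternative readings and should not be added together.
- **Misplacement is certain unless every subject responds.** Non-response is judged at the scheduled Day 29 visit, whose data carry the Week 4 label. A separate ET record is also needed, and its timing is unclear between footnote b and Protocol 7.2. Response includes minimal improvement, so the number terminated could be zero.
- **The primary endpoint is compromised.** SAP 17.1.2 protects it.
- **The DLQI summary is distorted by the windows.** Its carry-forward rule puts early values at Week 24 regardless.

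It is also fair to say that the study is exploratory and that listings show dates and study days, so a misplaced record would be visible. That helps a careful reader of the listings but does not correct the tables.

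**Conclusion.** The point holds as a conflict between rules whose most direct reading puts early data in the Week 24 row. Table B's label and the nominal-visit rule point to Week 24. Table B's day limits, Appendix 1 and SAP 17.2.2 point away from it. The exposure is confined to Week 24 or Day 169 secondary, safety and PK summaries and the Day 169 cytokine test.

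The size runs from 0% to 50% of the row for 0 to 5 early terminations. This assumes 10 subjects, a separate ET record for each early exit, and completion by everyone else. The documents give no expected number of non-responders, so no single value in that range is better supported than another. The SAP should be amended before the final analysis; the primary result does not depend on it.

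**What to change.** In the SAP:

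1. Remove ET from the Week 24 row of Table B.
2. Reserve Week 24 for visits made at Day 169, ±2 days or a stated wider window.
3. Report ET values in a separate ET or last-on-study row, and add that row to Appendix 1.
4. State in SAP 8.3 that nominal visit governs scheduled visits.

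A separate ET row makes contiguous windows unnecessary. If ET visits are instead mapped by actual study day, the windows must be contiguous. Mid-point cuts between clinic visits leave no uncovered day, but they give Week 4 the range Days 26 to 36 (upper cut (29 + 43)/2 = 36). An ET visit on Day 33 would then share a window with the Day 29 visit. A tie-break is needed: the scheduled visit takes precedence, so the Week 4 primary data are unchanged.

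The timing and obligation of the ET visit in footnote b and in Protocol 7.2 should be reconciled so that the label has one meaning.

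The cost is a SAP table edit and a programming rule, with no change to data collection. The Week 24 row will hold fewer observations, and these come from subjects who stayed in the study, so n should be shown beside each summary.

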8.5. STATISTICAL TESTS

This is an exploratory study and no formal hypothesis testing will be performed. Mean (SD) and nominal p-value will be reported where applicable. The data will be presented in summarized tabulated manner for trends and response patterns.

8.6. COMMON CALCULATIONS

8.6.1. CHANGE FROM BASELINE AT VISIT X

For numerical variables, change from Baseline at Visit X will be calculated as follows:

Change from Baseline = Test value at Visit X – Baseline value

8.6.2. PERCENT CHANGE FROM BASELINE AT VISIT X

Percent change from Baseline at Visit X will be calculated as follows:

Percent change from Baseline = (Test value at Visit X – Baseline value) / Baseline value x 100

